8.5 Primary Endpoint Analysis

The proportion of subjects with each value of “Occurred” or “No occurrences” or “Incomplete-Follow-up” will be summarized, as applicable, by treatment arm based on the ITT, mITT, Per Protocol and Modified Per Protocol analysis sets.

Superiority Testing

The following hypothesis will be tested for superiority:

$$\text{Null } H_0: \Delta_{\text{ciNPT-SOC}} = 0$$

$$\text{Alternative } H_a: \Delta_{\text{ciNPT-SOC}} \neq 0$$

where $\Delta_{\text{ciNPT-SOC}}$ is the difference in the proportion of subjects in the ciNPT arm with at least one SSC and the proportion of subjects in the SOC dressing arm with at least one SSC.

There are three populations including subpopulations: septic, aseptic and combined (septic + aseptic).

i) For the combined population, a Cochran-Mantel-Haenszel (CMH) test stratified by randomized type of revision (Septic, Aseptic) will be used to compare the SSC incidence rates between two treatment arms based on the mITT analysis set. The odds ratio and its asymptotic 95% confidence interval will be computed. This test is equivalent to the test of difference for the proportions. ii) For the septic and aseptic subpopulations, a Chi-square or Fisher's test, as appropriate will be performed within each randomized revision type for SSC incidence rates between treatment groups based on the corresponding mITT analysis set.

At the final analysis, a two-sided significance level of $\alpha = 0.048$ will be used to compare the SSC proportions between the two treatment arms after adjustment for the interim analysis.

Based on the interim analysis results, we will be considering three possible cases:

- Case 1: population was not enriched at interim analysis;
- Case 2: population was enriched by septic at interim analysis;
- Case 3: population was enriched by aseptic at interim analysis.

If the population is not enriched, then analyses described in Case 1 will be carried out. If the population is enriched, then analyses described in Case 2 or Case 3 will be carried out. If the population is enriched by increasing enrollment of one of the subpopulations based on statistical information, a closed testing strategy to ensure a strong control of type-1 error for the primary endpoint will be carried out based on two tests for the primary analysis.

The first test will utilize all subjects from the mITT combined population included in the interim and subjects post-interim. The second test will utilize only the post-interim mITT subjects from either the septic or aseptic population depending on the results and/or decision from the interim analysis. The second test will be performed only if the test 1 is statistically significant at the 0.048 level.

Case 1 Did Not Enrich	Case 2 Enriched with Septic	Case 3 Enriched with Aseptic

 • Test 1: Adaptive test of H_0 (Combined population) 	
 • Test 1: Adaptive test of H_0 (Combined population) • Test 2: standard test of H_0 (post-interim population only) 	
 • Test 1: Adaptive test of H_0 (Combined population) • Test 2: standard test of H_0 (post-interim population only)

For Case 1, if the 2-sided p-value from the test 1 is ≤ 0.048 and the SSC rate of the ciNPT arm is lower than the SSC rate of SOC arm, then the null hypothesis is rejected; superiority in effectiveness of the ciNPT arm compared with the SOC arm will be established. However, for Case 2 or Case 3, both test 1 and test 2 must reject the null hypothesis at the 0.048 level in order to claim statistical significance.

Additionally, figure(s) may be generated to display the results from the analyses of the primary endpoint graphically.

Supportive/exploratory analyses of the primary efficacy endpoint described below in Section 8.5.1 will be performed on the mITT analysis set unless otherwise specified.

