8.3.4. Analysis of Primary Endpoint

The analyses described in this section will be performed for the overall primary endpoint, “Any Surgical Site Complication (SSC)”, within 90 days of TKA revision, and repeated for each type of complication.

The proportion of subjects with each possible result – “Occurred”, “No occurrences”, or “Incomplete follow-up” will be reported, using the mITT Analysis Set as the denominator. See section 8.1.1 for definitions of these outcomes.

The comparative analysis of the primary endpoint will only consider subjects in the mITT Analysis Set, i.e., subjects with “Incomplete Follow-up” will be excluded. The proportions

of subjects with “Occurred” will be calculated within each treatment group and compared between treatment arms using a Cochran-Mantel-Haenszel (CMH) p-value stratified for type of revision (aseptic vs. septic). The difference between the proportions (ciNPT – SOC) and asymptotic 95% confidence interval will be computed. At the final analysis, a two-sided significance level adjusted for the interim efficacy analyses and potential sample size recalculation (e.g., $\alpha = 0.048$ if interim look is at $t=0.50$ and no sample size adjustment is made) will be used to compare the SSC proportions between the two treatment arms.

Supportive/exploratory analyses of the primary efficacy endpoint, SSC, may include:

- analyses comparing the treatment groups for the septic and aseptic revisions;
- analyses comparing the treatment groups for age, BMI, race/ethnicity, material used in the revision, and sex subgroups;
- analyses comparing the heterogeneity of the treatment groups across clinical sites;
- multivariable analyses comparing the treatment groups with covariate adjustment where possible covariates might include (but not limited to) age, BMI, sex, type of revision (aseptic or septic), and subject co-morbidities;
- Fisher’s exact test presenting the unstratified p-value;
- A repeat of any analysis above using the Per-Protocol and/or mPP Analysis Sets;

and other exploratory analyses as deemed appropriate.

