8.4. Additional Statistical Details

8.4.1. Hypothesis

This study will assess whether closed incision negative pressure therapy (ciNPT) reduces the surgical site complications (SSCs) compared to standard of care (SOC) among subjects who undergo a total knee arthroplasty (TKA) revision. The primary endpoint is measured by the proportion of subjects with SSC within 90 days of TKA revision among subjects in the mITT Analysis Set; the corresponding null and alternative hypotheses are:

Null: $\Delta_{\text{ciNPT-SOC}} = 0$

Alternative: $\Delta_{\text{ciNPT-SOC}} \neq 0$

where $\Delta_{\text{ciNPT-SOC}}$ is the difference in the proportion of subjects in the ciNPT group population with at least one SSC – proportion of subjects in the SOC dressing group with at least one SSC.

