8.4.2. Sample Size Determination

The primary endpoint of this study is the subject incidence of SSC as defined in section 4.11.1. The incidence rates of SSC are different for septic and aseptic revisions; the assumed SSC rate is 33% for septic and 6.9% for aseptic. This study plans to enroll at least 50% septic revisions overall. These enrollment rates lead to an assumed pooled SSC rate of 20% in the SOC dressing arm.

Assuming an overall type 1 error rate of 0.05, with a two-sided hypothesis test, the study will have at least 80% power to detect a difference of 10% (50% reduction) in SSCs in the ciNPT arm with 199 subjects in each treatment arm, with one interim analysis at about 50% of the evaluable subjects for a total of 398 subjects using the likelihood ratio test. With an estimated 5%-10% loss, a non-binding interim analysis for superiority at approximately 50% of the evaluable subjects using O'Brien-Fleming method for monitoring boundaries, the planned sample size will be inflated for potential loss of follow-up for a total of 440 subjects.

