6 INTERIM ANALYSIS

As stated in the protocol, an interim analysis will be conducted at information-time $t=0.5$, i.e., when approximately half the planned study subjects have had their primary endpoint assessed. The interim analysis will be performed at the $\alpha=0.0052$ level; if the p-value for the primary endpoint is < 0.0052 , the study will be stopped, and the null hypothesis rejected. Otherwise, the final analysis will be conducted at $\alpha=0.048$ (i.e., by constructing a 95.2% confidence interval) to preserve overall Type I error rate at 5%. These α values were chosen using an O'Brien-Fleming α -spending function assuming $t = 0.5$. The alpha levels that will be used at the interim and final will be calculated according to the precise information time at the interim analysis.

If warranted, based on the unblinded interim results, the final sample size may be increased using the appropriate statistical methodology as described in Chen et al. [2004]². Per Section 8.4.5 of the study protocol, it stated the increase to the final sample size would only occur if the interim results had a conditional power of success $\geq 50\%$, would be subject to the restrictions in Chen et al. [2004]², and

would not be considered statistically binding. However, the interim SAP further clarified that an increase to the final sample size could occur if the conditional power is below 50%. If the sample size is increased when conditional power is $\geq 50\%$, a type I error rate would not be inflated as mentioned in Chen et al. [2004]². If the sample size is increased when conditional power is $< 50\%$, an adjustment will be needed to control the Type I error. The adjustment was outlined in Section 7.3 of the interim SAP.

At the interim analysis, the rate of SSC for septic and aseptic revisions will be examined to confirm assumptions of the sample size calculations. In addition, the rate of SSC will be independently assessed for septic and aseptic revisions at the interim analysis to determine if a modification of enrollment from a 1:1 ratio of septic or aseptic revisions to focus on enrollment for either revision type is needed.

In the final analysis, the type I error rate ($\alpha=0.048$) for statistical significance will be used for the primary and secondary analyses using the O'Brien-Fleming method per study protocol.

Both, the interim SAP and the interim analysis results, will be included in the final clinical study report for this study.

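### SAP 8.5 and 8.6 name only an odds-ratio interval where the protocol plans an interval for the difference in proportions, the scale of the hypothesis and the power

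*SAP*

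**What the plan says.** **Protocol.** Section 8.3.4 plans the difference between the proportions, ciNPT minus SOC, and says its "asymptotic 95% confidence interval will be computed". Section 8.3.5 carries the same approach to any SSI and deep SSI. In 8.4.1 the parameter under test "is the difference in the proportion of subjects in the ciNPT group population with at least one SSC" minus the SOC proportion. Section 8.4.2 claims "power to detect a difference of 10% (50% reduction) in SSCs".

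**SAP.** Section 8.5 restates the hypothesis as a difference in proportions. For the combined population it then gives the CMH test and continues: "The odds ratio and its asymptotic 95% confidence interval will be computed. This test is equivalent to the test of difference for the proportions". Section 8.6.1 repeats this for any SSI, and 8.6.2 refers deep SSI to 8.6.1. No interval for the difference is named in these sections. For the septic and aseptic subpopulations, 8.5 and 8.6.1 name a Chi-square or Fisher test and no estimate.

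Section 10 lists the 8.5 change as a clarification, on the ground that the test is equivalent. Its only entry touching 8.6 concerns randomized versus actual revision type.

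Section 6 describes the final analysis at 0.048 as done "by constructing a 95.2% confidence interval", without saying for which parameter.

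**The concern.** The trial is designed around a 10-point absolute reduction. A reader of the results will want to know which absolute reductions the data support, and the SAP's endpoint sections plan no interval that answers this for the primary or the secondary endpoints. The reason given, test equivalence, does not reach estimation. A difference of zero and an odds ratio of one are the same null. Away from the null, the conversion from one scale to the other depends on the SOC rate, and the plan assumes very different SOC rates in the two revision types.

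The interval level is also inconsistent: 8.5 puts a 95% interval beside a test at 0.048, while section 6 speaks of 95.2%.

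**Working it through.** **1. Inputs (Protocol 8.4.2, SAP 2.1).** SOC SSC rate 33% septic and 6.9% aseptic; at least half septic; 20% v 10% overall; 199 per arm; two-sided overall alpha 0.05; power at least 80%. SAP 6 gives the final alpha as 0.048, so z = 1.977 for a 95.2% interval.

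**2. The plan's own figures reproduce.** Pooled SOC rate: 0.5 × 0.33 + 0.5 × 0.069 = 0.1995, stated as 20%. Sample size per arm for a difference in proportions:

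n = [1.960 × √(2 × 0.15 × 0.85) + 0.842 × √(0.2 × 0.8 + 0.1 × 0.9)]² / 0.10² = (0.990 + 0.421)² / 0.01 ≈ 199.

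A simulated likelihood ratio test with looks at 0.0052 and 0.048 gives 80.5% power at 199 per arm. No stated figure is wrong, and 199 per arm is a sample size for the difference.

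**3. Same effect, two scales.** Assumption: risk halved in both strata, 199 per arm split evenly (99.5 per arm per stratum), expected counts.

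- Septic, 16.5% v 33%: difference -16.5 points. SE = √[(0.165 × 0.835 + 0.33 × 0.67) / 99.5] = 0.0601. 95.2% CI -28.4 to -4.6. Odds ratio (0.165/0.835) / (0.33/0.67) = 0.40.
- Aseptic, 3.45% v 6.9%: difference -3.45 points. SE = √[(0.0345 × 0.9655 + 0.069 × 0.931) / 99.5] = 0.0313. 95.2% CI -9.6 to 2.7. Odds ratio 0.48.
- Combined difference, Mantel-Haenszel weights (here equal): (-16.5 - 3.45) / 2 = -9.98 points. SE = ½ × √(0.0601² + 0.0313²) = 0.0339. 95.2% CI -16.7 to -3.3.
- Combined Mantel-Haenszel odds ratio: (5.50 + 1.60) / (13.71 + 3.31) = 0.417. 95% CI 0.23 to 0.76 (Robins-Breslow-Greenland variance).

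The odds ratios are close, but the differences stand in the ratio 16.5 / 3.45 = 4.8.

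**4. Dependence on the septic/aseptic mix.** Assumption: 100 per arm at the interim, split evenly, then 99 per arm after it.

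| Post-interim subjects | Septic/aseptic per arm | Combined difference (points) | Odds ratio |
|---|---|---|---|
| half septic | 99.5/99.5 | -9.98 | 0.417 |
| 75% septic | 124.25/74.75 | -11.60 | 0.411 |
| all septic | 149/50 | -13.22 | 0.407 |
| 75% aseptic | 74.75/124.25 | -8.35 | 0.424 |
| all aseptic | 50/149 | -6.73 | 0.435 |

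For example, all septic: (149 × -16.5 + 50 × -3.45) / 199 = -13.22. The combined odds ratio hardly moves, while the combined difference follows the mix.

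**5. Test 2.** The documents give no post-interim stratum size. At an assumed 99 per arm of one type, expected events are 16.3 v 32.7 (septic) or 3.4 v 6.8 (aseptic). The aseptic counts are too small to rely on a Wald interval.

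**6. Agreement with the CMH test.** In 200,000 simulated trials for each of nine scenarios (no effect, one-third reduction, halving; three mixes; no interim adaptation), the 95.2% difference interval disagreed with the CMH test at 0.048 in 0.11% to 0.45% of trials. The SAP's 95% odds-ratio interval disagreed in 0.08% to 0.47%.

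**The case against.** **The interval in section 6 may be the missing one.** The hypothesis defines only a difference, so the unlabelled 95.2% interval can fairly be read as belonging to it. The table shells and the interim SAP are separate documents and might settle the matter. This stands as far as it goes: one cannot say that no difference interval will ever be produced. But 8.5 and 8.6.1 are where the analysis is specified, and they name the odds ratio.

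**The change was disclosed and is allowed.** True for 8.5: SAP 10 lists it, and Protocol 8.4.7 permits changes. A reader might infer concealment; the documents do not support that. What remains is that the stated reason does not justify the change and that 8.6 is not listed.

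**The odds ratio is the steadier pooled measure.** Step 4 bears this out, and a combined difference would also hide the contrast between revision types. That is a reason to keep the odds ratio and not a reason to omit the difference.

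**The septic, aseptic and Test 2 results.** Test 2 matters: "The second test will utilize only the post-interim mITT subjects from either the septic or aseptic population", and under enrichment "both test 1 and test 2 must reject the null hypothesis at the 0.048 level". A reader might infer that the SAP dropped estimates promised for these comparisons. It did not. Protocol 8.3.4 plans an interval for the overall difference, lists the septic and aseptic comparisons among analyses that may be done, and does not contain Test 2. Estimates there would be an addition.

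**The decision rule.** A reader might also infer that the primary test or its type I error is compromised. Nothing here shows that; the CMH test of no effect is the same whichever measure is reported.

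**Conclusion.** The point holds as one of estimation and reporting. For the primary and both secondary endpoints, the SAP's analysis sections name an odds-ratio interval where the protocol plans a difference with its interval, and the equivalence they cite covers only the test. Arm-level proportions are still to be tabulated, so a crude difference could be derived by hand, but without a pre-specified interval.

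At the planning rates, the quantity left without a clearly planned interval is about -10.0 points (95.2% CI -16.7 to -3.3). The contrast of 4.8 to 1 between strata assumes the same relative effect in both; it is simply 33/6.9 and not a prediction. The mix and Test 2 figures rest on assumed post-interim enrollment. No stated design figure changes. The correction is worth making because it is nearly free and lets the trial report the effect it was sized to detect.

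**What to change.** **In SAP 8.5 and 8.6**

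1. Report the risk difference (ciNPT minus SOC) with its confidence interval for the combined population, alongside the odds ratio. The protocol names no estimator, so specify one: a Mantel-Haenszel difference with the same revision-type stratification as the CMH test it accompanies (randomized type in 8.5; randomized and actual type in 8.6, following 8.6.1).
2. For the primary endpoint, set both the difference and the odds-ratio intervals at 1 minus the final alpha. Section 6 already provides for this to vary: "The alpha levels that will be used at the interim and final will be calculated according to the precise information time".
3. Limit the equivalence sentence to the test of the null.
4. Keep the planned tests as the decision rule. State that intervals after enrichment or re-sizing are descriptive.

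**In SAP 10**

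5. List the odds-ratio change for 8.6 as well as for 8.5.

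**Optional, beyond what the protocol promised**

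6. Give the septic and aseptic differences and, if enrollment is enriched, the difference in the Test 2 subjects. Use a small-sample interval such as Newcombe or Miettinen-Nurminen, given the roughly 3 v 7 aseptic events expected at 99 per arm.

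**Cost.** A few estimates from the same tables, plus wording; SAP 6 allows amendment before the final database lock. The downside is that an interval may occasionally disagree with the CMH test. The rates in step 6 are small, but they do not cover the adaptive test, which is why item 4 is needed.

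### The primary effect estimate carries a 95% interval, although the plan ties its final 0.048 test to a 95.2% interval: a small reporting inconsistency that leaves the decision rule intact

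*SAP*

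**What the plan says.** Two levels are given for the interval that accompanies one comparison.

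- **95.2%.** SAP 6 says that, if the trial does not stop at the interim, the final analysis is run at 0.048 "by constructing a 95.2% confidence interval", and gives preservation of the 5% overall error as the reason. Protocol 8.4.5 says the same. Both add that the levels will be recalculated from the actual information time.
- **95%.** Protocol 8.3.4: "The difference between the proportions (ciNPT – SOC) and asymptotic 95% confidence interval will be computed". SAP 8.5 replaces the difference with an odds ratio and keeps the level: "The odds ratio and its asymptotic 95% confidence interval will be computed". SAP 10 records that replacement and repeats 95%.

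The test is stated separately. SAP 8.5 says that a two-sided level of 0.048 "will be used to compare the SSC proportions between the two treatment arms after adjustment for the interim analysis". It then gives the rule for a trial without enrichment: reject "if the 2-sided p-value from the test 1 is ≤ 0.048 and the SSC rate of the ciNPT arm is lower" than the SOC rate. If the population is enriched (Cases 2 and 3), two tests must both reject at 0.048.

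**The concern.** A 95% interval corresponds to a 0.05 test, which this plan does not use at its final analysis. A programmer working from SAP 8.5 would not produce the interval that SAP 6 describes. The interval in the results table would take no account of the interim look. When the p-value falls just above 0.048, that interval may lie wholly on the side of benefit while the primary test has failed. The trial report would then carry a headline estimate that suggests superiority next to a formal result that denies it. At stake is the consistency of the reported primary result, not the control of error.

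**Working it through.** **Inputs.** Overall two-sided alpha 0.05, 199 evaluable per arm, SOC rates 33% (septic) and 6.9% (aseptic), half septic, 50% reduction (SAP 2.1). One look at t = 0.5, levels 0.0052 and 0.048 (SAP 6). CMH test stratified by revision type (SAP 8.5).

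**1. The plan's own levels.** For a classical two-look O'Brien-Fleming boundary, solve P(|Z1| > C√2 or |Z2| > C) = 0.05 with correlation √0.5. This gives C = 1.9774. The nominal levels are 2[1 - Φ(1.9774 × √2)] = 0.00517 and 2[1 - Φ(1.9774)] = 0.04799. The stated 0.0052 and 0.048 reproduce, and 1 - 0.048 = 95.2%.

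**2. Width.** The multipliers are 1.9774 (95.2%) and 1.9600 (95%), a ratio of 1.0089. At the pooled design rates (10% vs 20%, 199 per arm):

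- OR = (0.1/0.9)/(0.2/0.8) = 0.444
- SE of log OR = √(1/19.9 + 1/179.1 + 1/39.8 + 1/159.2) = 0.295
- 95% interval: 0.249 to 0.793
- 95.2% interval: 0.248 to 0.797

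**3. A dataset in which interval and test disagree.** Septic 17/100 (ciNPT) vs 29/100 (SOC); aseptic 7/99 vs 9/99.

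- CMH: observed minus expected = (17 - 23) + (7 - 8) = -7. Variance = 8.90 + 3.70 = 12.59. |z| = 7/√12.59 = 1.972, p = 0.0486. The test does not reject at 0.048.
- Mantel-Haenszel OR = (17×71/200 + 7×90/198)/(83×29/200 + 92×9/198) = 9.217/16.217 = 0.568.
- 95% interval: 0.323 to 0.9996, which excludes 1.
- 95.2% upper limit: 1.005, which includes 1 and agrees with the test.

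**4. How often.** Simulation of 400,000 trials with 100 septic and 99 aseptic per arm, no interim stopping and no enrichment. The test is CMH without continuity correction. The interval is Mantel-Haenszel with Robins-Breslow-Greenland variance; this is an assumption, since the SAP names no variance formula.

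| Event | Design effect | Null |
|---|---|---|
| 0.048 < p ≤ 0.05 | 0.40% | 0.22% |
| 95% interval excludes 1, test does not reject | 0.11% | 0.11% |
| 95% interval includes 1, test rejects | 0.01% | 0 |
| 95.2% interval excludes 1, test does not reject | 0 | 0 |
| 95.2% interval includes 1, test rejects | 0.37% | 0.09% |

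The p-value band is therefore not the same as the contradiction. Only about a quarter of trials in the band contradict the test at the design effect (0.106/0.399), and about half under the null (0.112/0.218).

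**5. Error rate.** With levels 0.0052 and 0.048 the overall two-sided error is 0.0500. It would be 0.0520 if the final decision were taken at 0.05, that is, from a 95% interval.

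**The case against.** The strongest reply is that SAP 8.5 decides on the p-value and never lets the 95% interval decide. SAP 6 still names the 95.2% interval, so the 95% one can be read as conventional estimation alongside it. The first half stands. A reader might infer from the 0.0520 above that the plan inflates type I error. The documents do not support that, because the final level is 0.048 wherever a decision is described. The second half is a possible reading, but no section states it, and SAP 8.5 gives the 95% interval as the only one for the primary estimate.

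A second reply concerns the remedy. A Wald-type odds ratio interval is not the inverse of the CMH test, so matching the levels does not guarantee agreement. At the design effect, total disagreement rises from about 0.12% of trials (0.106% + 0.012%) to about 0.37%. This stands. All of the remaining disagreement is in the conservative direction, where the interval includes 1 although the test has rejected. The direction that overstates the result disappears.

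It would also be tempting to conclude that superiority should be read from the 95.2% interval. That goes too far. It would displace the stratified test and lose the roughly 0.4% of trials just described. Nor could a single interval on the combined population carry the two-test requirement of Cases 2 and 3.

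**Conclusion.** The inconsistency is real and minor. The interval level in Protocol 8.3.4, SAP 8.5 and SAP 10 does not match the level that Protocol 8.4.5 and SAP 6 attach to the final analysis. The 95% interval is about 0.9% too short by the plan's own standard, and it excludes no effect without rejection in about 0.1% of trials under either hypothesis. It would be too strong to say that every p-value between 0.048 and 0.05 produces a contradiction; most such trials at the design effect do not.

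The frequencies rest on the design rates, an even septic/aseptic split, a Mantel-Haenszel interval, and no stopping or enrichment. The figure of 95.2% rests on a look at t = 0.5. At another information time the matching level changes. If no interim were held and the final level were 0.05, a 95% interval would be the right one.

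**What to change.** In Protocol 8.3.4, SAP 8.5 and SAP 10:

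- Set the primary interval at 100(1 - actual final two-sided alpha)%, noting that this is 95.2% when the final level is 0.048.
- Label any 95% interval that is also shown as descriptive and not adjusted for the interim look.
- State that the CMH p-value rule, including the two-test rule in Cases 2 and 3, alone decides superiority.

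The cost is a few words in three places and one confidence-level setting in the program. SAP 1 and SAP 6 allow such an amendment before database lock. The downside is an interval about 0.9% wider, which can include 1 despite rejection in about 0.4% of trials at the design effect. The third item is what keeps such a case from being misread.
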